| 10.7.2. Other Secondary Efficacy Endpoints | 
Replaced the endpoint: “The proportion of subjects achieving clinical remission at Week 52 and corticosteroid-free since Weeks 16, 24, 32, 40 and 48” with the following endpoint: “The proportion of subjects who had not received corticosteroids for \geq 4 weeks and achieved clinical remission at Week 52 among subjects receiving corticosteroids at baseline”
 | 
Expanded the endpoint to analyze subjects in clinical remission at the end of the study (Week 52) who were corticosteroid-free for \geq 4 weeks at any time during the study. This analysis will enable an evaluation of the impact of etrasimod on achieving clinical remission while eliminating the use of corticosteroids.
 |
| [REDACTED] | [REDACTED] | [REDACTED] |
| 14.1. Investigator Responsibilities | 
Revised sentences below as follows: “The Investigator will disclose to the Sponsor sufficient, accurate, financial information to allow the Sponsor to submit accurate disclosure statements to the FDA per 21 Code of Federal Regulations (CFR) Part 54 (Financial Disclosure by Clinical Investigators) or to other regulatory authorities that have similar requirements.” “The Investigator is responsible for compliance with applicable sections of ICH GCP requirements.” “The Investigator may also be responsible for compliance with 21 CFR Part 312, Subpart D, (Responsibilities of Investigators) and other ICH GCP requirements, federal, and local laws, applicable to conducting drug studies.” “An Investigator will, in accordance with the provisions of ICH GCP guidelines and/or 21 CFR Part 50, obtain the informed consent of each human subject to whom the drug is administered.”
 | 
Updated language to reflect Arena standard protocol language for this section and account for current standards
 |

| Section No. and Name | Description of Change | Brief Rationale |
|----------------------------------------------------------------------------------------------------------------------------|--------------------------------------------------------------------------------------------------------------------------------------------------------------------------------------------------------------------------------------------------------------------------------------------------------------------------------------------------------------------------------------------------------------------------------------------------------------------------------------------------------------------------------------------------------------------------------------------------------------------------------------------------------------------------------------------------------------------------------------------------------------------------------------------------------------------------------------------------------------------------------------------------------------------------------------------------------------------------------------------------|-----------------------------------------------------------------------------------------------------------------|
| 14.2. Sponsor Responsibilities | 
Revised the paragraph as follows:
 
“The Sponsor is responsible for compliance with applicable sections of ICH E6(R2) and 21 CFR Part 312, Subpart D (Responsibilities of Sponsors). The Sponsor is responsible for selecting qualified Investigators, providing them with the information they need to conduct an investigation properly, and ensuring proper monitoring of the investigation(s). Sponsors are also responsible for ensuring the investigation(s) is conducted in accordance with the general investigational plan and protocols contained in the Investigational New Drug (IND) application (or equivalent), maintaining an effective IND (or equivalent) with respect to the investigations, and ensuring the FDA (and/or other regulatory authorities as applicable), other applicable health authorities, and all participating Investigators are promptly informed of significant new adverse effects or risks with respect to the drug.”
 | Updated language to reflect Arena standard protocol language for this section and account for current standards |
| Appendix 1: Schedules of Assessments, Table 7: Schedule of Assessments, Screening and 12-Week Treatment Period, Footnote a | 
Added the following sentence:
 
“All visits beyond W0/D1 may be virtual or hybrid visits (Section 9.6).”
 | Updated to account for modifications in Section 9.6 (see above) |

| Section No. and Name | Description of Change | Brief Rationale |
|------------------------------------------------------------------------------------------------------------------------------------------------|--------------------------------------------------------------------------------------------------------------------------------------------------------------------------------------------------------------------------------------------------------------------------------------------------------------------------------------------------------------------------------------------------------------------------------------------------------------------------------------------------------------------------------------------------------------------------------------------------------------------------------------------------------------------------------------------------------------------------------------------------------------------------------------------------------------------------------|--------------------------------------------------------------------------------------------------------------------------------------------------|
| Appendix 1: Schedules of Assessments, Table 7: Schedule of Assessments, Footnotes p and q | 
Split footnote “p” into “p” and “q” as follows:
 
^p A PFT will include FEV₁ and FVC measurements. When available, DLCO measurements will also be performed (when DLCO is not available, sites should consult the Sponsor or Sponsor’s delegate).
 
^q The Screening pulmonary function test (PFT) should be done within the 28-Day Screening period. PFTs should be performed ± 7 days during the study treatment period and posttreatment period (ie, 2-Week Follow-Up visit). PFTs occurring at the ET visit that are within 4 weeks of the last assessment (eg, Week 12), will only be required if clinically indicated. The 2-Week Follow-Up visit assessment is only required if clinically indicated. Details regarding additional PFTs are provided in Section 9.10.4.
 | To delineate and clarify the PFT timing information for the specific PFT assessments |
| Appendix 1: Schedules of Assessments, Table 8: Schedule of Assessments | Revised column header as follows: “W52/D365 ± 14 Days/Early Termination ^a ± 7 Days” | To enable critical visit assessments to be made in the event that facilities are inaccessible due to various logistic or operational constraints |
| Appendix 1: Schedules of Assessments Table 7: Schedule of Assessments, Footnote y Table 8: Schedule of Assessments, Footnote o | Added “Biomarker sample collection is not required at Early Termination visit.” | Footnote added to clarify sample collection needed at Early Termination |
| Appendix 1: Schedules of Assessments, Table 7: Schedule of Assessments, Footnote r Table 8: Schedule of Assessments, Footnote h and Footnote i | Revised second sentence in the footnote to: “The 2-Week Follow-Up visit assessment is only required if clinically indicated.” | To reduce patient burden, the necessity of conducting OCTs during follow up is only required if clinically indicated |

APPENDIX 1: PROGRAMMING CONVENTIONS FOR OUTPUTS61

APPENDIX 2: PARTIAL DATE CONVENTIONS63

APPENDIX 3: [REDACTED]63

APPENDIX 4: IBDQ SCORING RULES71

APPENDIX 5: SF-36 SCORING RULES72

APPENDIX 6: WPAI-UC SCORING RULES73

APPENDIX 7: CLASSIFICATION OF RESCUE THERAPY74

LIST OF TABLES

Table 1: List of Primary and Key Secondary Estimands13

Table 2: Visit Windows for Efficacy and Safety Analyses20

Table 3: Planned Analyses by Endpoint39

Table 4: Markedly Abnormal Criteria for Vital Signs54

LIST OF FIGURES

Figure 1: Study Design16

Figure 2: Gatekeeping Procedure Summary24

LIST OF ABBREVIATIONS AND DEFINITIONS OF TERMS

Abbreviation	Explanation
5-ASA	5-aminosalicylic acid
AE	adverse event
AESI	adverse events of special interest
ALC	absolute lymphocyte count
ALP	alkaline phosphatase
ALT	alanine aminotransferase
APD334	etrasimod
Arena	Arena Pharmaceuticals, Inc.
AST	aspartate aminotransferase
ATC	Anatomical Therapeutic Chemical
AV	atrioventricular
β-hCG	beta-human chorionic gonadotropin
BLQ	below the limit of quantitation
BMI	body mass index
bpm	beats per minute
CI	confidence interval
CM	concomitant medication
CMH	Cochran-Mantel-Haenszel
COVID-19	coronavirus disease 2019
CR	copy reference
CRP	C-reactive protein
CS	clinically significant
CSR	clinical study report
CTCAE	Common Terminology Criteria for Adverse Events
C _{trough,ss}	average steady-state trough plasma concentration
CV	coefficient of variation
DBP	diastolic blood pressure
DLCO	diffusing capacity of the lungs for carbon monoxide
EAIR	exposure-adjusted incidence rate
ECG	electrocardiogram

Abbreviation	Explanation
eCRF	electronic case report form
eDISH	evaluation of drug-induced serious hepatotoxicity
EIM	extraintestinal manifestation
ES	endoscopic score
FAS	Full Analysis Set
FCP	fecal calprotectin
FCS	fully conditional specification
FDA	Food and Drug Administration
FEF	forced expiratory flow
FEV ₁	forced expiratory volume in 1 second
FVC	forced vital capacity
GGT	gamma-glutamyl transferase
HR	heart rate
HRQoL	health-related quality of life
hs-CRP	high-sensitivity C-reactive protein
IBDQ	Inflammatory Bowel Disease Questionnaire
ICF	informed consent form
JAK	Janus kinase
LLQ	lower limit of quantitation
LOESS	locally estimated scatterplot smoothing
LS	least squares
MAR	missing at random
MCMC	Markov Chain Monte Carlo
MedDRA	Medical Dictionary for Regulatory Activities
mFAS	modified Full Analysis Set
MMRM	mixed-effect model with repeated measures
MMS	modified Mayo score
MNAR	missing not at random
NCS	not clinically significant
NHI	Nancy Histological Index
NRI	nonresponder imputation

Abbreviation	Explanation
NRS	numeric rating scale
OCT	optical coherence tomography
OLE	open-label extension
PFT	pulmonary function test
PGA	Physician's Global Assessment
PK	pharmacokinetics
PRES	posterior reversible encephalopathy syndrome
PT	preferred term
RB	rectal bleeding
RHI	Robarts Histopathology Index
RNA	ribonucleic acid
SAE	serious adverse event
SAP	statistical analysis plan
SBP	systolic blood pressure
SD	standard deviation
SDTM	Study Data Tabulation Model
SE	standard error
SF	stool frequency
SF-36	Medical Outcomes Study 36-Item Short Form Health Survey
SI	International System of Units
SOC	system organ class
ss	steady state
TB	tuberculosis
TEAE	treatment-emergent adverse event
TLC	total lung capacity
TME	targeted medical event
TMS	total Mayo score
TNF α	tumor necrosis factor alpha
UC	ulcerative colitis
ULN	upper limit of normal
ULQ	upper limit of quantitation

Abbreviation	Explanation
WHO	World Health Organization
WPAI-UC	Work Productivity and Activity Impairment Questionnaire – Ulcerative Colitis

1. INTRODUCTION

This Statistical Analysis Plan (SAP) describes the statistical rationale, methods, rules, and conventions to be used in the presentation and analysis of efficacy, safety, pharmacokinetic (PK), and efficacy-related biomarker data for Clinical Study Protocol APD334-301. It describes the data to be summarized and analyzed, including specifics of the statistical analyses to be performed (ICH 1998). This SAP is based on the Clinical Study Protocol Amendment 4.0, dated 22 December 2020.

Analyses of the genetics (Clinical Study Protocol APD334-301 Section 9.9) [REDACTED] data will be specified in a separate biomarker analysis plan.

2. STUDY OBJECTIVES

2.1. Primary Objective

The primary objective is to assess the efficacy of etrasimod on clinical remission in subjects with moderately to severely active ulcerative colitis (UC) after 12 and 52 weeks of treatment.

2.2. Secondary Objectives

The secondary objective is to assess the efficacy of etrasimod on clinical response, symptomatic response and remission, endoscopic changes, corticosteroid-free remission, and mucosal healing in subjects with moderately to severely active UC at timepoints up to 52 weeks of treatment.

2.3. Safety Objectives

The safety objective is to assess the long-term safety of etrasimod after daily doses of 2 mg for up to 52 weeks in subjects with moderately to severely active UC.

2.4. Other Objectives

Other objectives include evaluation of etrasimod PK and the effect of etrasimod on health-related subject-reported outcomes and biomarkers.

2.5. Estimands

The primary and key secondary efficacy estimands to support regulatory decisions are described in Table 1. The analyses will be performed on the Full Analysis Set (FAS) as defined in Section 5.3. Other secondary efficacy variables (specified in Section 16.3.1) will have the population, intercurrent event handling strategy and population-level summary measure similar to the primary estimand. Supplementary analyses for the primary and the key secondary estimands will be performed on the modified Full Analysis Set (mFAS) and the Per Protocol populations, respectively (ICH 2019). Intercurrent events include: 1) initiate a rescue medication for UC, 2) have an increase in dose over Baseline levels in their existing UC medication, or 3) have a rescue non-drug treatment (eg, colectomy, ileostomy, or sigmoidectomy) before the

efficacy assessment. Refer to [APPENDIX 7](#) for the definition of rescue therapies (medication and medical procedures).

Table 1: List of Primary and Key Secondary Estimands

Estimand	Definition	Attribute			
		Population	Variable/Endpoint	Intercurrent Event Handling Strategy	Population-Level Summary Measure
Primary Estimand 1	Efficacy of etrasimod on clinical remission at Week 12	Randomized subjects who receive at least 1 dose of study treatment and with Baseline MMS 5 to 9	The proportion of subjects with SF = 0 (or = 1 with a ≥ 1 -point decrease from Baseline), RB = 0, and ES ≤ 1 (excluding friability) at Week 12	Subjects with any of the 3 intercurrent events ^a before the efficacy assessment will be treated as nonresponders.	Difference between etrasimod and placebo in the endpoint at Week 12
Primary Estimand 2	Efficacy of etrasimod on clinical remission at Week 52	Randomized subjects who receive at least 1 dose of study treatment and with Baseline MMS 5 to 9	The proportion of subjects with SF = 0 (or = 1 with a ≥ 1 -point decrease from Baseline), RB = 0, and ES ≤ 1 (excluding friability) at Week 52	Subjects with any of the 3 intercurrent events ^a before the efficacy assessment will be treated as nonresponders.	Difference between etrasimod and placebo in the endpoint at Week 52
Key Secondary Estimand 1	Efficacy of etrasimod on endoscopic improvement at Week 12	Randomized subjects who receive at least 1 dose of study treatment and with Baseline MMS 5 to 9	The proportion of subjects with ES of ≤ 1 (excluding friability) at Week 12	Same as the intercurrent event handling strategy for the primary estimand	Difference between etrasimod and placebo in the endpoint at Week 12
Key Secondary Estimand 2	Efficacy of etrasimod on endoscopic improvement at Week 52	Randomized subjects who receive at least 1 dose of study treatment and with Baseline MMS 5 to 9	The proportion of subjects with ES of ≤ 1 (excluding friability) at Week 52	Same as the intercurrent event handling strategy for the primary estimand	Difference between etrasimod and placebo in the endpoint at Week 52
Key Secondary Estimand 3	Efficacy of etrasimod on symptomatic remission at Week 12	Randomized subjects who receive at least 1 dose of study treatment and with Baseline MMS 5 to 9	The proportion of subjects with SF = 0 (or = 1 with a ≥ 1 -point decrease from Baseline) and RB = 0 at Week 12.	Same as the intercurrent event handling strategy for the primary estimand	Difference between etrasimod and placebo in the endpoint at Week 12

Estimand	Definition	Attribute			
		Population	Variable/Endpoint	Intercurrent Event Handling Strategy	Population-Level Summary Measure
Key Secondary Estimand 4	Efficacy of etrasimod on symptomatic remission at Week 52	Randomized subjects who receive at least 1 dose of study treatment and with Baseline MMS 5 to 9	The proportion of subjects with SF = 0 (or = 1 with a ≥ 1 -point decrease from Baseline) and RB = 0 at Week 52.	Same as the intercurrent event handling strategy for the primary estimand	Difference between etrasimod and placebo in proportion of responders at Week 52
Key Secondary Estimand 5	Efficacy of etrasimod on corticosteroid-free clinical remission at Week 52	Randomized subjects who receive at least 1 dose of study treatment and with Baseline MMS 5 to 9	The proportion of subjects with clinical remission at Week 52 and who had not been receiving corticosteroids for ≥ 12 weeks prior to Week 52	Same as the intercurrent event handling strategy for the primary estimand	Difference between etrasimod and placebo in proportion of responders at Week 52
Key Secondary Estimand 6	Efficacy of etrasimod on sustained clinical remission	Randomized subjects who receive at least 1 dose of study treatment and with Baseline MMS 5 to 9	The proportion of subjects with sustained clinical remission (clinical remission at both Weeks 12 and 52)	Same as the intercurrent event handling strategy for the primary estimand	Difference between etrasimod and placebo in proportion of responders
Key Secondary Estimand 7	Efficacy of etrasimod on mucosal healing at Week 12	Randomized subjects who receive at least 1 dose of study treatment and with Baseline MMS 5 to 9	The proportion of subjects with ES of ≤ 1 (excluding friability) with histologic remission measured by a Geboes Index score < 2.0 at Week 12	Same as the intercurrent event handling strategy for the primary estimand	Difference between etrasimod and placebo in proportion of responders at Week 12
Key Secondary Estimand 8	Efficacy of etrasimod on mucosal healing at Week 52	Randomized subjects who receive at least 1 dose of study treatment and with Baseline MMS 5 to 9	The proportion of subjects with ES of ≤ 1 (excluding friability) with histologic remission measured by a Geboes Index score < 2.0 at Week 52	Same as the intercurrent event handling strategy for the primary estimand	Difference between etrasimod and placebo in proportion of responders at Week 52

^a Intercurrent events include: 1) initiate a rescue medication for UC, 2) have an increase in dose over Baseline levels in their existing UC medication, or 3) have a rescue non-drug treatment (eg, colectomy, ileostomy, or sigmoidectomy) before the efficacy assessment. Refer to [Appendix 7](#) for the definition of rescue therapies (medication and medical procedures). ES, endoscopic score; RB, rectal bleeding; SF, stool frequency; UC, ulcerative colitis.

3. STUDY DESIGN

3.1. General Description

[figure not shown]
This is a multicenter, randomized, double-blind, placebo-controlled study to evaluate the efficacy and safety of etrasimod 2 mg in subjects with moderately to severely active UC. The study consists of a 28-Day Screening Period, a 12-Week Treatment Period, a 40-Week Treatment Period, and a 2-Week and 4-Week Follow-Up Period. The study design diagram can be found in [Figure 1](#). Eligible subjects will be randomized (2:1 ratio) to receive either etrasimod (2 mg once daily) or matching placebo (once daily) in a double-blind fashion for up to 52 weeks of treatment. Randomization will be stratified by (a) naïve to biologic or Janus kinase (JAK) inhibitor therapy at study entry (Yes or No), (b) Baseline corticosteroid use (Yes or No), and (c) Baseline disease activity (modified Mayo score [MMS]: 4 to 6 or 7 to 9).

Approximately 420 subjects are planned to be enrolled. The target subject population will include (approximately 50% of subjects in each of the following categories):

1. Subjects who have had an inadequate response, loss of response, or intolerance to conventional therapy and are naïve to biologic or JAK inhibitor therapy
2. Subjects who have had an inadequate response, loss of response, or intolerance to a biologic or JAK inhibitor (subjects in this category may have received prior conventional therapy)

At the end of the 12-Week Treatment Period, subjects will undergo Week 12 efficacy and safety assessments and be evaluated for clinical response/remission as well as UC disease worsening. Subjects whose UC condition in the opinion of the Investigator has not improved or has worsened, compared with Baseline (Week 0/Day 1), as defined in Clinical Study Protocol APD334-301 Section 5.1.1 and who meet other eligibility criteria will have the option to enter an open-label extension (OLE) study (Study APD334-303). Subjects must complete Week 12 to be eligible for the OLE. Subjects who do not meet disease worsening criteria, including those demonstrating clinical response/remission at Week 12 will continue into the 40-Week Treatment Period and continue their double-blind treatment. Subjects who either experience disease worsening in the 40-Week Treatment Period or complete all study procedures at Week 52 will have the option to enroll into the OLE study if they meet all eligibility criteria. Subjects who do not participate in the OLE study will have 2-Week and 4-Week Follow-Up visits after their last treatment administration/Early Termination (ET) visit. The study design is outlined in [Figure 1](#).

Figure 1: Study Design

JAK, Janus kinase; UC, ulcerative colitis

3.2. Schedules of Assessments

Schedules of Assessments can be found in Clinical Study Protocol APD334-301 Appendix 1.

3.3. Changes to Analysis from Protocol

The primary analysis set for the efficacy endpoints is updated to the Full Analysis Set with MMS 5 to 9. Subgroup definition related to MMS is updated accordingly. The entire FAS will be used in supplementary analyses.

Definition of histologic improvement based on Geboes in Section 16 is updated from Geboes Index score < 3.1 to Geboes Index score ≤ 3.1.

The criterion of “Exclusion of other causes for loss of response unrelated to underlying UC (eg, infection)” is removed from the definition of “loss of response” in Section 16 since a more conservative approach is used.

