4.1. Inclusion Criteria

Subjects must meet ALL of the following inclusion criteria to be eligible for enrollment into the study:

1. Men or women 16 to 80 years of age, inclusive, at the time of assent/consent. Enrollment of subjects < 18 years should be conducted only if acceptable according to local laws and regulations
2. Ability to provide written informed consent or assent (parent or legal guardian must provide consent for a subject < 18 years of age who has assented to participate in the study or as required per local regulations) and to be compliant with the schedule of protocol assessments

Disease-specific inclusion criteria:

3. Diagnosed with UC \geq 3 months prior to screening. The diagnosis of UC must be confirmed by endoscopic and histologic evidence. The endoscopy and histology report should be present in the source documents; however, if not available, the screening endoscopy and histology may serve as such
4. Active UC confirmed by endoscopy with \geq 10 cm rectal involvement. Subjects with proctitis only at baseline who meet the other eligibility criteria for inclusion, including the endoscopic and rectal bleeding criteria for moderate to severe disease, will be capped at 15% of the total subjects enrolled

5. Moderately to severely active UC defined as MMS of 4 to 9, including an ES of ≥ 2 and RB score ≥ 1
6. Received a surveillance colonoscopy (performed according to local standard) within 12 months before baseline to rule out dysplasia in subjects with pancolitis > 8 years duration or subjects with left-sided colitis > 12 years duration. Subjects without a surveillance colonoscopy within the prior 12 months will have a colonoscopy at screening (ie, in place of screening proctosigmoidoscopy). Any adenomatous polyps must be removed according to routine practice prior to their first dose of study treatment.

Prior treatment:

7. Demonstrated an inadequate response to, loss of response to, or intolerance to at least 1 of the following therapies as defined below:

Conventional therapy

- a. Oral 5-aminosalicylic acid (5-ASA) compounds
- b. Corticosteroids
- c. Thiopurines

Biologic therapy or JAK inhibitor therapy

- a. Antitumor necrosis factor alpha (TNF α) antibodies (eg, infliximab, adalimumab, golimumab, or biosimilars)
- b. Anti-integrin antibodies (eg, vedolizumab)
- c. Anti-interleukin 12/23 antibodies (eg, ustekinumab)
- d. JAK inhibitors (eg, tofacitinib)

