10.2. Determination of Sample Size

Based on a 2-group Fisher's exact test, a 1-sided significance level of 0.025, and a 2:1 randomization ratio, 420 total subjects (280 etrasimod, 140 placebo) are required to achieve 93.4% power to detect a difference of 13.5% in the primary endpoint of clinical remission at Week 52 between the etrasimod treatment group (23.5%) and the placebo treatment group

(10.0%). With this sample size, there will be 96% power to detect a difference of 12.5% in the other primary endpoint of clinical remission at Week 12, assuming a placebo rate at 6.0%. The lower bound of overall power for both primary endpoints (as coprimary endpoints) is at least 90%; and since the two primary endpoints are expected to be at least moderately positively correlated, the actual overall power to reject both of their null hypotheses is likely to be greater than 90%.

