7. DETERMINATION OF SAMPLE SIZE

Based on a 2-group Fisher’s exact test, a 1-sided significance level of 0.025, and a 2:1 randomization ratio, 420 total subjects (280 etrasimod, 140 placebo) are required to achieve 93.4% power to detect a difference of 13.5% in the primary endpoint of clinical remission at Week 52 between the etrasimod treatment group (23.5%) and the placebo treatment group (10.0%). With this sample size, there will be 96% power to detect a difference of 12.5% in the other primary endpoint of clinical remission at Week 12, assuming a placebo rate at 6.0%. The lower bound of overall power for both primary endpoints (as coprimary endpoints), is at least 90%; since the 2 primary endpoints are expected to be at least moderately, positively correlated, the actual overall power to reject both of their null hypotheses is likely to be greater than 90%. Workbook calculations from EAST® 6 statistical software are included below.

Design: Discrete Endpoint: Two-Sample Test - Parallel Design - Fisher's Exact

Test Parameters	
Design ID	Week 52 Clin Rem
Test Type	2-Sided
Specified α	0.05
Power	0.934
Sample Size (n)	420
Model Parameters	
Proportion Treatment (π_t)	0.235
Proportion Control (π_c)	0.1
$\delta = \pi_t - \pi_c$	
Under H0	0
Under H1	0.135
Allocation Ratio (n_t/n_c)	2

Sample Size Information

Sample Size (n)	420
Treatment (n _t)	280
Control (n _c)	140

Design: Discrete Endpoint: Two-Sample Test - Parallel Design - Fisher's Exact

Test Parameters	
Design ID	Week 12 Clin Rem
Test Type	2-Sided
Specified α	0.05
Power	0.96
Sample Size (n)	420
Model Parameters	
Proportion Treatment (π_t)	0.185
Proportion Control (π_c)	0.06
$\delta = \pi_t - \pi_c$	
Under H0	0
Under H1	0.125
Allocation Ratio (n_t/n_c)	2

⊖ **Sample Size Information**

Sample Size (n)	420
Treatment (n _t)	280
Control (n _c)	140

8. STATISTICAL CONSIDERATIONS**8.1. Multicenter Studies**

This study will be conducted by multiple investigators at multiple centers internationally. Randomization to treatment groups is stratified by:

- Naïve to biologic or JAK inhibitor therapy at study entry (Yes or No)
- Baseline corticosteroid use (Yes or No)
- Baseline disease activity (MMS: 4 to 6 or 7 to 9)

Data from all sites will be pooled and statistical analyses will not be adjusted for investigational site, country, or geographic region.

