16.1.3. Primary Analysis of Primary Efficacy Variables

The following hypotheses (H_{01} and H_{02}) for the coprimary endpoints will be tested:

H_{01} : The proportion of subjects achieving clinical remission at Week 12 is the same between etrasimod and placebo.

H_{11} : The proportion of subjects achieving clinical remission at Week 12 is different between etrasimod and placebo.

H_{02} : The proportion of subjects achieving clinical remission at Week 52 is the same between etrasimod and placebo.

H_{12} : The proportion of subjects achieving clinical remission at Week 52 is different between etrasimod and placebo.

Both hypotheses will be tested at the 2-sided α level, 0.05.

The primary efficacy analysis will be performed for the FAS with Baseline MMS 5 to 9. The Cochran-Mantel-Haenszel (CMH) test will be used, stratified by naïve to biologic or JAK inhibitor therapy at study entry (Yes or No), Baseline corticosteroid use (Yes or No), and Baseline disease activity (MMS: 4 to 6 or 7 to 9). Reported randomization stratum will be used in the model. Results will be expressed as the number and percentage of subjects in remission, difference in remission percentages and 95% CI and p-value, odds ratio and 95% CI. If there are no responders in both treatment groups in any stratum, the difference in remission percentages and associated inferences can still be made. However, the odds ratio and its CI may be calculated from the unstratified CMH.

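### The stated power is for all 420 subjects with Baseline MMS 4 to 9, but the primary test uses only MMS 5 to 9; even at 420 the plan's Fisher figures give a joint lower bound of 89.4%, not 90%

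*SAP*

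**What the plan says.** Protocol 4.1, criterion 5, sets eligibility: "Moderately to severely active UC defined as MMS of 4 to 9". About 420 such subjects are planned (SAP 3.1).

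SAP 3.3 then narrows the set for the primary test: "The primary analysis set for the efficacy endpoints is updated to the Full Analysis Set with MMS 5 to 9". Table 1 and Sections 16 and 16.1.3 of the SAP agree, and the whole FAS is kept for supplementary analyses only.

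SAP 7 carries over the protocol's sample size section: "420 total subjects (280 etrasimod, 140 placebo) are required to achieve 93.4% power to detect a difference of 13.5% in the primary endpoint". It adds 96% power at Week 12. Protocol 10.2 and SAP 7 both conclude that the "lower bound of overall power for both primary endpoints (as coprimary endpoints) is at least 90" percent. Both then cite an expected positive correlation as the reason that actual joint power is likely to be higher still.

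On the test, SAP 7 reads "Based on a 2-group Fisher’s exact test, a 1-sided significance level of 0.025, and a 2:1 randomization ratio". The software output printed below it shows a two-sided test at 0.05, and SAP 16.1.3 says "Both hypotheses will be tested at the 2-sided α level, 0.05".

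**The concern.** There are two separate faults.

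- **Wrong set.** The power is computed as if all 420 subjects entered the primary test. Every subject with a Baseline MMS of 4 reduces the number tested. Neither document gives an expected share of such subjects or an allowance for them, and SAP 7 was not recalculated when SAP 3.3 changed the set.
- **Wrong bound.** A lower bound on joint power of at least 90% cannot be obtained from marginal powers of 93.4% and 96%.

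Joint power is the figure the trial depends on. Overall success requires both co-primary null hypotheses to be rejected (SAP 8.4), and key secondary testing opens only then (Protocol 10.12.1). The Amendment 4 summary of changes gives reaching at least 90% joint power as one of the reasons for enrolling 420.

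**Working it through.** **Inputs**

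- Week 52 remission rates: 23.5% etrasimod, 10.0% placebo (SAP 7).
- Week 12 remission rates: 18.5% etrasimod, 6.0% placebo (SAP 7, software output).
- Subjects: 280 and 140, allocated 2:1 (SAP 7).
- Test: Fisher's exact, as in the plan's own calculation.
- Share of subjects with MMS 4: not in the documents; assumed from 0% to 15%.

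**Step 1. Reproduce the plan's figures.** Exact power was found by enumerating both binomial distributions at 280 versus 140.

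| Fisher's exact test | Week 52 | Week 12 |
|---|---|---|
| Two-sided 0.05 (software output) | 93.44% | 95.98% |
| One-sided 0.025 (SAP text) | 92.76% | 95.55% |

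The two-sided setting reproduces the stated 93.4% and 96%.

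**Step 2. Joint lower bound at 420.** With P1 and P2 the marginal powers, the bound that needs no assumption about dependence is P1 + P2 - 1.

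- Stated figures: 0.934 + 0.960 - 1 = 0.894.
- Independence: 0.934 × 0.960 = 0.897.
- Most favourable rounding of the stated figures: 0.9345 + 0.965 - 1 = 0.8995.
- One-sided test as worded in the text: 0.9276 + 0.9555 - 1 = 0.883.

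None reaches 0.90. The bound first passes 90% at about 426 analysed subjects (284 versus 142): 0.9382 + 0.9625 - 1 = 0.9007.

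**Step 3. Remove the MMS 4 subjects.** Planning rates and the 2:1 ratio are held; the test is two-sided Fisher at 0.05. The last column uses a bivariate normal model with correlation 0.5.

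| Assumed MMS 4 share | Analysed (etrasimod:placebo) | Week 52 | Week 12 | Joint lower bound | Joint power, correlation 0.5 |
|---|---|---|---|---|---|
| 0% | 420 (280:140) | 93.4% | 96.0% | 89.4% | 90.7% |
| 5% | 399 (266:133) | 92.0% | 94.9% | 86.9% | 88.6% |
| 10% | 378 (252:126) | 90.8% | 93.5% | 84.3% | 86.6% |
| 15% | 357 (238:119) | 89.1% | 92.7% | 81.7% | 84.5% |

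**Step 4. Change the test.** The planned primary test is a stratified Cochran-Mantel-Haenszel (CMH) test, so the step was repeated with an unstratified chi-square test. The bound is then 90.6% at 420 and 88.4% with 5% excluded. With correlation 0.5, joint power is 89.9% at 5% excluded and 88.1% at 10%.

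**The case against.** - **The shortfall at 420 is small.** It is 0.6 percentage points. With the stated marginal powers, joint power passes 90% at a correlation of about 0.25 (90.04%) and is 90.7% at 0.5, so the plan's remark that actual joint power is likely to exceed 90% is plausible at 420. This stands. It does not rescue the lower bound, because the plan offers correlation only as a reason to expect more than the bound.
- **Fisher's test is conservative for a CMH analysis.** This also stands in part: under chi-square the bound at 420 exceeds 90%. But the stated powers are Fisher figures, and chi-square does not keep the bound above 90% once 5% are excluded.
- **The size of the loss is not known.** The MMS 4 share is absent, and the documents do not say which MMS range the planning rates describe. Rates in MMS 5 to 9 could differ in either arm, and enrolment is only approximately 420. All of this is fair, and it is a reason to recalculate rather than to leave the old figures in place.
- **Nothing in the analysis changes.** SAP 3.3 declares the new set openly, and the MMS 4 to 9 analysis is kept as supplementary. This is true, and it limits the weight of the point, but a stated power should describe the test to be performed.

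**Conclusion.** The concern holds on both counts. The stated powers belong to a larger set than the one tested, and the claimed joint lower bound of at least 90% is not supported by the plan's own marginal powers: it is 89.4% at 420. The analysis-set mismatch is the weightier part. If 5% to 15% of subjects have an MMS of 4, the bound is between 86.9% and 81.7%. That range assumes the planning rates carry over unchanged to MMS 5 to 9, exactly 420 subjects treated at 2:1, and a two-sided Fisher test at 0.05. The individual powers for 420 reproduce correctly. The validity of the test and type I error control are not in question. The correction should be made, but it does not undermine the design.

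**What to change.** In SAP 7, restate the Week 52 power, the Week 12 power and the joint power for the number of subjects with Baseline MMS 5 to 9, a count that can be taken from blinded data before database lock. Name the test and its sidedness, so that the text and the software output agree. Replace the claim of a lower bound of at least 90% with the computed value (89.4% at 420, lower for fewer subjects). If a joint power above the bound is quoted, give the correlation assumed. Keep the original 420-subject calculation as the record of how the sample size was chosen, labelled as covering MMS 4 to 9.

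Add a sentence to SAP 3.3 saying that the power in Protocol 10.2 was computed for the full MMS 4 to 9 population; this avoids a protocol amendment. The cost is SAP wording and one rerun of the power calculation. There is no extra enrolment, no unblinding and no change to the test or alpha. On the planning rates, the stated power becomes less favourable.
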